We hypothesize that administration of TXA will reduce perioperative bleeding in osteotomy procedure with minimal side effects. As a result, swelling and postoperative pain will decrease thus improving postoperative outcomes. While TXA has been used in various orthopedic surgeries to reduce bleeding, no study has investigated the efficacy of TXA during a TTO procedure and TXA during HTOs have limited available studies. The available literature shows perioperative bleeding and hematoma significantly decreased during HTO procedures³. By comparing high tibial osteotomy patients to tibial tubercle osteotomy patients, we will determine if there is a difference in efficacy or if both cohorts will be similarly affected.

Study Design

This is a single-center, prospective cohort study. Patients will be assigned to their cohorts based on diagnosis and appropriate treatment as determined by the surgeon. Patients will be consented in the study once they are scheduled for either a HTO or TTO, therefore this will not be a randomized study. The study is comparing blood loss and postoperative pain after TXA administration in patients receiving a high tibial osteotomy (HTO) to patients receiving a tibial tubercle osteotomy (TTO) with or without medial patello-femoral ligament (MPFL) reconstruction. One gram of intravenous tranexamic acid will be administered before tourniquet inflation and 1 gram of IV TXA before closure of the incision. Patients will be asked on postoperative day 1, 2 and 7 to rate their pain according to the VAS scale. Patients will have their knee swelling measured immediately postoperatively and at their one-week follow up visit. The swelling ratio is defined as the postoperative mean circumference of upper pole of patella and lower pole of patella divided by the preoperative values.

Primary Objective

The primary objective of the study is to determine if there are any differences in blood loss between patients undergoing high tibial osteotomy (HTO) and tibial tubercle osteotomy (TTO) with or without medial patello-femoral ligament (MPFL) reconstruction.

Secondary Objective

Secondary objective of the study is to determine if there is a difference in post operative pain and swelling between patients undergoing HTO compared to patients undergoing TTO.

II. CHARACTERISTICS OF THE RESEARCH POPULATION

Number of Subjects

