Patients indicated and scheduled for a high tibial osteotomy or tibial tubercle osteotomy with or without medial patello-femoral ligament reconstruction will be identified from faculty surgeon case logs at the NYU Langone Health, Langone Orthopedic Hospital Sports Medicine Division. After informed consent is obtained, a chart review of patients' medications and past medical histories will be reviewed based on their electronic medical records to identify any current pain medications or exclusion criteria. Patients will be in the study for 1 week, until their first follow up visit.

Patients will be given 1 gram of intravenous tranexamic acid (TXA) before tourniquet inflation and 1 gram of IV TXA before closure of the incision. Immediate post-operative management will not be affected by this study. The study team will not be blinded to the study as there is no randomization to each cohort. All patients will receive a standardized regimen of aspirin for DVT prophylaxis and Percocet for pain management, which is standard of care post-operative treatment.

Information to be recorded pre-operatively includes age, sex, height, weight, BMI, and American Society of Anesthesiology (ASA) classification. Intra-operative information will also be recorded, including operative time, and estimated blood loss. During the surgery, a suction device is utilized to remove excess blood from the surgical site and sucked into the suction drain and placed into a measuring cup. We will measure the perioperative blood loss by look at the measuring cup and seeing how much blood is inside. Knee swelling postoperatively will be measured using the swelling ratio. The swelling ratio was defined as the circumference of the operative limb divided by the circumference of the contralateral limb. Pain severity scores at rest will be assessed by use of a visual analog scale (VAS; 0 = no pain, 10 = worst pain imaginable) at 0.5, 1, 1.5, 2, 4, 6, 24, and 48 hours as well as 7 days after surgery. Percocet consumption will be recorded at 24 hours, 1 day, 2 days and 7 days after surgery. Incidence of TXA-related side effects (nausea/vomiting, itching, anxiety, increased thirst, rapid heartbeat) in the first 24 hours will be noted. Time to discharge from the post-anesthesia care unit (PACU) and time to discharge from the hospital will be recorded.

Analysis and Data Monitoring

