Data monitoring will be done by [name], the principal investigator. He will review the following accumulated data quarterly.

He will monitor whether or not:

1. Collection and storage of patient data was performed in a sensitive and secure manner, as defined in the informed consent form and protocol, ensuring information is stored on REDCap.
2. All study activities were conducted with primary emphasis on patient care and wellbeing, ensuring the patients are not in discomfort and have an abnormally high VAS following the surgery.
3. If there were any adverse events, and if so were addressed appropriately and per protocol
4. The risk/benefit to patients has remained the same throughout the course of the study.

The study will be stopped if there are unexpected severe AE's in more than one patient. Adverse events will be defined as negative reactions to the intravenous TXA during or after surgery, including seizures, vision problems. We will submit summaries of data and safety monitoring annually.

Data Analysis

According to a post hoc power analysis calculating the effect size using our preliminary data, >15 patients are required with $d=0.6$ to obtain a power of 0.80 and an alpha value of 0.05. Therefore we are including an additional 5 patients per group to account for patients that may be

lost to follow up. Statistical analysis will be performed using chi-squared and/or fisher's exact testing depending on size for binary variables. Continuous variables will be compared with paired t-tests if the data is approximately normally distributed. If the data is not normally distributed, Mann-Whitney tests will be used. All protected health information will be removed prior to statistical analysis. We will use patient subjective pain, perioperative blood loss and knee swelling data as statistical endpoints. Subjective pain will be measured with the VAS (visual analogue scale), perioperative blood loss will be measured looking at blood loss from the suction drain after surgery. The swelling ratio is defined as the postoperative mean circumference of upper pole of patella and lower pole of patella divided by the preoperative values according to our previous study. The endpoints must be statistically significant between the two cohorts to show TXA is effective.

Data Storage and Confidentiality

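### The success rule credits TXA with any HTO-versus-TTO difference, although both cohorts receive the same TXA and there is no comparator without it

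*Combined protocol and SAP*

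**What the plan says.** The statements that bear on this point are in three sections of the combined protocol and SAP.

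- **Success criterion** (III, Data Analysis): "The endpoints must be statistically significant between the two cohorts to show TXA is effective". The endpoints listed there are pain, perioperative blood loss and knee swelling. No other criterion for efficacy is given.
- **Cohorts** (I, Study Design): "Patients will be assigned to their cohorts based on diagnosis and appropriate treatment as determined by the surgeon", and "therefore this will not be a randomized study".
- **TXA exposure** (III, Methods and Procedures): "Patients will be given 1 gram of intravenous tranexamic acid (TXA) before tourniquet inflation", with a second administration before closure. Study Design describes the same regimen. Neither section distinguishes HTO from TTO patients.
- **Hypothesis** (I, Rationale): "We hypothesize that administration of TXA will reduce perioperative bleeding in osteotomy procedure with minimal side effects". The Rationale adds that, by comparing the two groups, "we will determine if there is a difference in efficacy or if both cohorts will be similarly affected".
- **Primary objective** (I): "The primary objective of the study is to determine if there are any differences in blood loss between patients undergoing high tibial osteotomy" and those undergoing tibial tubercle osteotomy.

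The protocol names no group that does not receive TXA, whether concurrent, placebo or historical.

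**The concern.** The hypothesis asks what happens with TXA compared with no TXA. The primary objective asks how HTO compares with TTO when everyone has TXA. The success criterion answers the first question with data that address only the second.

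This goes wrong in both directions. If HTO and TTO bleed differently for surgical or patient reasons and TXA does nothing, the criterion can still be met. If TXA works equally well in both operations, it produces no difference between cohorts, and the criterion counts that as efficacy not shown. The Rationale treats that second outcome, both cohorts similarly affected, as a legitimate finding, so the protocol also disagrees with itself.

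The stated interest in a difference in efficacy meets the same obstacle: efficacy within each operation is never estimated, so the two efficacies cannot be compared. What is at stake is the conclusion. Section IV (Potential Benefits) hopes the results will inform the efficacy of TXA and possibly change standard of care. Followed as written, the plan can produce such a statement regardless of whether TXA works.

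**Working it through.** **1. What the contrast estimates.** Write the expected outcome in each cohort, in SD units, as the procedure's own level minus the TXA effect in that procedure:

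- HTO: μ_H − τ_H
- TTO: μ_T − τ_T
- Difference: Δ = (μ_H − μ_T) − (τ_H − τ_T)

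If τ_H = τ_T, the TXA terms cancel and Δ is the procedure gap alone. If τ_H ≠ τ_T, the difference in effects enters Δ but cannot be separated from μ_H − μ_T, because no patient goes without TXA.

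**2. Inputs.** From the protocol: 20 per cohort (Number of Subjects), alpha 0.05 (Data Analysis), three endpoints. Assumed: two-sided testing (sidedness is not stated); a two-sample t-test with equal SDs, because the cohorts are independent (the protocol writes paired t-tests, or Mann-Whitney if not normal); and the size of the procedure gap, which the documents do not give.

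**3. The plan's own figure.** The protocol gives no operating characteristics for the criterion. Its sample-size statement (more than 15 patients for d = 0.6, power 0.80) does not reproduce for two independent groups, where a two-sided t-test needs 45 per group. That is a separate problem, and nothing below depends on it.

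**4. Chance that one endpoint is significant.** The t statistic is noncentral t with 2n − 2 degrees of freedom and noncentrality Δ√(n/2). For n = 20, √(20/2) = 3.162.

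| True situation (SD units) | Δ | Noncentrality | P(significant) |
|---|---|---|---|
| TXA no effect, procedure gap 0.5 | 0.5 | 1.58 | 34% |
| TXA no effect, gap 0.6 | 0.6 | 1.90 | 46% |
| TXA no effect, gap 0.8 | 0.8 | 2.53 | 69% |
| TXA no effect, gap 1.0 | 1.0 | 3.16 | 87% |
| TXA reduces bleeding by 1.0 in both, gap 0.6 | 0.6 | 1.90 | 46% |
| TXA reduces bleeding by 1.0 in both, no gap | 0 | 0 | 5% |
| TXA worsens bleeding by 1.0 in both, no gap | 0 | 0 | 5% |
| TXA effect 0.6 in HTO only, no gap | −0.6 | −1.90 | 46% |
| TXA effect 0.6 in HTO only, gap 0.6 | 0 | 0 | 5% |

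Rows 2 and 5 give the same probability for a useless TXA and a highly effective one. The last two rows show that an unequal TXA effect can be exposed or hidden entirely by the procedure gap. A simulation with 100,000 replicates agreed with the exact values to within half a percentage point in the scenarios simulated (all rows except gaps 0.5 and 0.8).

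**5. If five per group are lost.** The protocol adds five per group for loss to follow-up, so 15 per group is the planned lower case. With a useless TXA and gaps of 0.5, 0.8 and 1.0, the probabilities become 26%, 56% and 75%.

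**6. More than one endpoint.** The criterion does not say whether all three endpoints must be significant or any one. Assume independent endpoints, the same gap on each, a useless TXA and n = 20:

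- All three: 0.338³ = 4%, 0.693³ = 33%, 0.869³ = 66% for gaps of 0.5, 0.8 and 1.0.
- Any one: 1 − 0.662³ = 71%, 1 − 0.307³ = 97%, 1 − 0.131³ = more than 99%.
- Any one with no gap at all: 1 − 0.95³ = 14%.

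**7. Reading a null result as similarity.** The 95% CI half-width is t(0.975, 38) × √(2/20) = 2.024 × 0.316 = 0.64 SD, already wider than the planning effect of 0.6. A non-significant estimate can lie anywhere up to about 0.64 SD from zero, so its interval can extend to nearly 1.28 SD. With 15 per group the half-width is 2.048 × √(2/15) = 0.75 SD.

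**The case against.** Several points can fairly be made in the plan's favour.

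- **Necessary, not sufficient.** Literally, the sentence makes significance a requirement for showing efficacy, not proof of it. That is a correct reading, and the false-positive figures rest on treating the criterion as sufficient. Since no other criterion is given, that is how it would be applied. As a necessary condition alone it still fails, because it rejects a TXA that works equally well in both operations.
- **The endpoints are plural.** If all three must be significant, the false-positive figures fall to 4%, 33% and 66% under independence. This changes the size of the error, not its nature.
- **An unequal TXA effect would move the contrast.** True. The accurate statement is that the design cannot attribute a difference to TXA, rather than that TXA can never influence the result.
- **Other reference data exist.** Data Analysis mentions preliminary data and a previous study, but only for the effect size and the swelling definition. A preoperative circumference is not a no-TXA comparator either.
- **Similarity is partly inferred.** The protocol does not say that a non-significant test will be read as similar effects. That part is a caution about interpretation, not a stated error.
- **The objectives are sound.** The primary and secondary objectives are HTO-versus-TTO contrasts and can be addressed. This stands: the defect lies in the interpretation rule and the hypothesis, not in the data to be collected.

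**Conclusion.** The concern holds. With TXA given to everyone and cohorts defined by operation, the effect of TXA is not identifiable, and a criterion that rests proof of efficacy on the HTO–TTO difference is wrong as written. That conclusion is structural: it depends on no assumed effect size and would be the same with any number of patients.

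The percentages only illustrate how far the criterion can mislead. For a single endpoint at 20 per cohort, it would credit an inert TXA 34% to 87% of the time for procedure gaps of 0.5 to 1.0 SD, and would credit a TXA equally effective in both operations 5% of the time when there is no gap. They rest on a two-sided two-sample t-test, on assumed gaps, and on reading the criterion as sufficient. The requirement for one or all endpoints, and losses to follow-up, shift them as shown in the working.

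This must be corrected before results are interpreted, because it determines what the trial may conclude.

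**What to change.** Delete the success criterion in Data Analysis and replace it with wording such as:

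> The analysis estimates the difference in blood loss, pain and swelling between HTO and TTO patients, all of whom received TXA, with 95% confidence intervals. It does not test whether TXA is effective, and a non-significant difference will not be read as similarity.

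In the same edit:

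- Restate the hypothesis in the Rationale so that it matches the primary objective.
- Reword the Rationale sentence about a difference in efficacy, which the design cannot address.
- Bring the Purpose paragraph and the efficacy statement under Potential Benefits into line.

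The cost is protocol wording. Cohorts, sample size, data collection and the primary objective stay as they are. The trial gives up an efficacy claim that its design could not support. If efficacy is the real aim, wording will not be enough: the study would need a comparator without TXA within each operation, which is a different design with its own sample size.

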Data recorded from this study will be organized in RedCap and maintained on the department's secure password-protected research drive until the data are de-identified. Participant medical information will only be available to the principal investigator and research staff as necessary for data analysis. All patient health information will be de-identified and assigned a code. Information linking participants' names, social security numbers and medical record numbers will be stored in a secure location separate from the medical information. This information will be destroyed at study closure.

Adverse Event Reporting

Information about any breach of confidentiality will be documented in the electronic data collection system and/or on the paper CRFs, as appropriate. It will be the responsibility of the Principal Investigator to report any Serious Adverse Event (SAE) that occurs during the data collection to the Institutional Review Board (IRB) within the timeframe specified by NYU SoM.

IV. RISK/BENEFIT ASSESSMENT

Risk

This study involves risk of medication side effects as well as a breech of confidentiality.

Intravenous TXA can cause the following side effects:

- Anxiety
- blurred vision
- changes in vision
- chest pain
- confusion
- cough
- dizziness or lightheadedness
- fainting
- fast heartbeat
- greatly increased or decreased frequency of urination or amount of urine
- increased thirst
- loss of appetite
- nausea or vomiting

- numbness of the hands
- pain, redness, or swelling in the arm or leg
- sudden shortness of breath or troubled breathing

Rare side effects include:

- Convulsions or seizures
- Orthostatic hypotension
- sweating
- trouble seeing
- unusual tiredness or weakness.

Protection against Risks

The patients will stay in the recovery unit a minimum of 3 hours after surgery as the mean duration of the effect of TXA is 3 hours and be monitored by the recovery unit nurses^{15,16}. Patients will be instructed to call the principal investigator and visit the emergency department if there are any symptoms of calf swelling or chest pain within the first seven days following surgery.

All patients will be de-identified and given a code. Information linking the patient codes to the participants' names and medical record numbers will be stored in a secure location separate from the medical information. Access to the information linking the linkage codes with participant identifiers shall be restricted.

Potential Benefits to the Subjects

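### The protocol states no route by which seizures, vision changes, sudden breathlessness, fainting or confusion after the recovery stay reach the investigator, although it lists all five as TXA effects

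*Combined protocol and SAP*

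**What the plan says.** Four parts of the protocol bear on how side effects become known.

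- **Patient instruction** (section IV, Protection against Risks): patients are to telephone the investigator and also go to emergency care "if there are any symptoms of calf swelling or chest pain within the first seven days following surgery". Both actions are asked for, and two symptoms are named. The same paragraph provides for nurse monitoring first: "The patients will stay in the recovery unit a minimum of 3 hours after surgery". The reason given is that the drug acts for 3 hours on average.
- **Risk list** (section IV, Risk): 21 entries, of which 16 are general and 5 rare. They include "sudden shortness of breath or troubled breathing", fainting, confusion, "changes in vision" and "Convulsions or seizures".
- **Adverse-event definition** (section III, Analysis and Data Monitoring): "Adverse events will be defined as negative reactions to the intravenous TXA during or after surgery, including seizures, vision problems". Severe events that are unexpected, in two or more patients, stop the study.
- **Scheduled data collection** (section I, Study Design; section III, Methods and Procedures): TXA side effects are noted for the first 24 hours under five headings: nausea or vomiting, itching, anxiety, thirst and rapid heartbeat. Later contacts are described as follows: "Patients will be asked on postoperative day 1, 2 and 7 to rate their pain according to the VAS scale". Percocet use is recorded at the same days, and knee circumference is measured at the one-week visit.

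**The concern.** The protocol defines adverse events to include those arising after the operation and gives two examples, seizures and vision problems. A patient who had either at home would find neither among the symptoms named in the instruction, and no planned contact is described as asking about them. The same holds for sudden breathlessness, fainting and confusion, which the risk list attributes to the drug.

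Two things are at stake. One is safety oversight: the principal investigator's quarterly review and the duty to report serious events to the IRB act only on events that have become known. The other is the reported result. The hypothesis includes that TXA has minimal side effects, and a low adverse-event count would be read as support for it. If the count is low partly because nobody asked, that reading is not sound.

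**Working it through.** The protocol states no figure on this point, so there is none to reproduce. The check sets the sections side by side.

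**Step 1. Where each event appears**

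| Event | Risk list | Example in adverse-event definition | Patient instruction | 24-hour checklist | Described content of day 1, 2, 7 contacts |
|---|---|---|---|---|---|
| Sudden breathlessness | yes | no | no | no | no |
| Fainting | yes | no | no | no | no |
| Confusion | yes | no | no | no | no |
| Vision changes | yes | yes | no | no | no |
| Seizures | yes (rare) | yes | no | no | no |
| Chest pain | yes | no | yes | no | no |
| Calf swelling | in part (limb swelling) | no | yes | no | no |

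The first five events are on the risk list and in none of the last three columns. Both examples in the adverse-event definition are among them. The checklist is also out of step in the other direction: itching is on it but not on the risk list.

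**Step 2. What the timetable covers**

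Recovery-unit nurses observe the patient for at least 3 hours. The five-symptom record ends at 24 hours. Study participation is one week, 7 × 24 = 168 hours, so no side-effect record of any kind is scheduled for 168 − 24 = 144 hours. This is a length of time, not a share of risk. The documents do not suggest that risk is constant over the week.

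**Step 3. What happens afterwards**

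Quarterly review (Analysis and Data Monitoring) and reporting of serious events to the IRB (Adverse Event Reporting) both come after an event is known. Neither section says how an event at home becomes known.

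**Step 4. Illustration of the possible undercount**

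Inputs: n = 40 (Number of Subjects). Assumed, because the documents give neither: p, the share of patients with such an event after the recovery stay; and c, the share of those events that reach the record.

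Expected recorded count = 40 × p × c. With full and then half capture:

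- p = 2%: 0.8 and 0.4
- p = 5%: 2 and 1
- p = 10%: 4 and 2

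Chance that at least two patients have a recorded event = 1 − (1 − pc)^40 − 40·pc·(1 − pc)^39:

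| p | c = 1 | c = 0.75 | c = 0.5 | c = 0.25 |
|---|---|---|---|---|
| 2% | 0.190 | 0.121 | 0.061 | 0.017 |
| 5% | 0.601 | 0.445 | 0.264 | 0.089 |
| 10% | 0.920 | 0.812 | 0.601 | 0.264 |

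For example, with p = 5% and c = 0.5, pc = 0.025 and the result is 1 − 0.975^40 − 40 × 0.025 × 0.975^39 = 0.264. The table shows how incomplete capture thins a count in a study of this size. It is not an estimate for this trial, and it does not describe the stopping rule, which counts a narrower class of event.

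**The case against.** The strongest reply is that the protocol is not the whole of what patients are told. Section VI says they will be made aware of risks and asked to explain them back before consenting, and Methods and Procedures leaves immediate postoperative care unchanged. The consent form is not in the text available here and may carry wider instructions. A reader might infer that patients are told to act *only* on calf swelling and chest pain. The documents do not say so; they name two symptoms and are silent on others. That part of the reply stands. It does not supply a collection step, because explaining a risk at consent is not the same as asking about it afterwards.

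A second reply is that the plan separates acute drug effects, watched for during the recovery stay, from later ones, covered by the seven-day warning. This is a reasonable reading, and early events would probably be seen in recovery. But 3 hours is given as a mean, the checklist runs to 24 hours, and the adverse-event definition has no end time short of the study week.

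Third, an event could come to light unprompted at the one-week visit. It could, so events can go unreported, not that they will.

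Two further inferences are tempting and not supported:

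- **That the stopping rule is disabled.** The rule counts unexpected severe events. "Unexpected" is not defined, and effects already on the risk list may not qualify, so the link to stopping is uncertain.
- **That 2 warned symptoms against 21 listed effects measures the gap.** Chest pain and limb swelling are on both sides, three entries concern vision, and several, such as thirst, cough and sweating, are minor.

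Nor does a short warning contradict a longer risk list. The difficulty is a missing collection route.

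**Conclusion.** The point holds as a gap in adverse-event ascertainment. Five effects that the protocol itself lists, including both examples in its adverse-event definition, have no stated route to the investigator once the monitored recovery stay ends. The adverse-event count can therefore be too low. By how much cannot be said, since the documents give neither an event rate nor a capture share.

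The conclusion assumes that the day 1, 2 and 7 contacts are limited to what is described for them, and that no other text, such as the consent form, sets up adverse-event collection. If the consent form or case report forms already contain such a question, the remaining work is to bring the protocol into line with them. I would class this as a cheap improvement.

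**What to change.** Reconcile four texts: the 24-hour checklist in Methods and Procedures, the adverse-event definition in Analysis and Data Monitoring, and the risk list and patient instruction in section IV. State in the protocol how events after the recovery stay are elicited and recorded.

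Add an adverse-event question, covering at least the events the plan itself names, to the existing day 1, 2 and 7 contacts, and record the answer whether positive or negative so that a zero count means that patients were asked. Which symptoms should prompt a call or an emergency visit is a clinical matter for the sponsor and investigator, and nothing is proposed on it here.

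The cost is a protocol wording change and a short question at contacts already planned, with no new visits. The recorded adverse-event count may be somewhat higher as a result, and the report should say that patients were asked directly.
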